² Complicated diarrhea defined by the presence of symptoms such as cramping, nausea/vomiting, ≥ grade 2, decreased performance status, pyrexia, sepsis, neutropenia ≥ grade 3, frank bleeding, and/or dehydration requiring intravenous fluid substitution. Patients with complicated diarrhea should be evaluated for pembrolizumab mediated autoimmune colitis with additional management as specified for pembrolizumab.

³ Loperamide should be made available prior to start of study treatment soloperamide administration can begin at the first signs of diarrhea.

⁴ Escalation of trametinib to previous dose level is allowed after consultation with the study chair and in the absence of another episode of complicated or severe diarrhea in the 4 weeks subsequent to dose reduction.

Table 13. Dose Modification Guidelines and Management for Rash

Rash Severity	Management Guideline	Dose Modification
Grade 1	 Initiate prophylactic and symptomatic treatment measures.¹ Use moderate strength topical steroid.² Reassess after 2 weeks. 	 Continue trametinib. If rash does not recover to baseline within 2 weeks despite best supportive care, reduce trametinib by one dose level.³
Grade 2	 Initiate prophylactic and symptomatic treatment measures.¹ Use moderate strength topical steroid.² Reassess after 2 weeks. 	 Reduce trametinib by one dose level. If rash recovers to ≤ grade 1 within 2 weeks, increase dose to previous dose level. If no recovery to ≤ grade 1 within 2 weeks, interrupt trametinib until recovery to ≤ grade 1. Restart trametinib at reduced dose level.
Grade ≥3	 Use moderate strength topical steroids. Consider oral methyl- prednisolone dose pack.² Consider consulting dermatologist. 	 Interrupt trametinib until rash recovers to ≤ grade 1. Then restart pembrolizumab and trametinib (reduced by one dose level).³ If no recovery to ≤ grade 2 within 4 weeks, permanently discontinue trametinib and pembrolizumab.

Rash prophylaxis is recommended for the first 6 weeks of study treatment.

Moderate-strength topical steroids: Hydrocortisone 2.5% cream or fluticasone priopionate 0.5% cream. Trametinib may be escalated to previous dose level if no rash is evident 4 weeks after restarting study treatment.

Table 14. Pneumonitis Guidelines

CTCAE Grade	Adverse Event Management	Action and Dose Modification
Grade 1	 CT scan (high-resolution with lung windows) recommended. Work-up for infection. Monitoring of oxygenation via pulse- oximetry recommended. Consultation with pulmonologist recommended. 	Continue trametinib at current dose.
Grade 2	 CT scan (high-resolution with lung windows). Work-up for infection. Consult pulmonologist. Pulmonary function tests: If < normal, repeat every 8 weeks until ≥ normal. Bronchoscopy with biopsy and/or BAL recommended. Symptomatic therapy including corticosteroids if clinically indicated. 	 Interrupt trametinib and pembrolizumab until recovery to grade ≤1. If AE resolved to Grade ≤1 and relationship to trametinib and or pembrolizumab is equivocal, restarting pembrolizumab and trametinib (with dose reduction at investigators discretion) may be considered, after discussion with the study chair. If treatment delay is > 4 weeks, permanently discontinue trametinib and pembrolizumab.
Grade 3	 CT scan (high-resolution with lung windows). Work-up for infection. Consult pulmonologist. Pulmonary function tests-if < normal, repeat every 8 weeks until ≥ normal. Bronchoscopy with biopsy and/or BAL if possible. Symptomatic therapy including corticosteroids as clinically indicated. 	Permanently discontinue trametinib and pembrolizumab.
Grade 4	• Same as grade 3.	Permanently discontinue trametinib and pembrolizumab.

Dose Reduction Scheme for Trametinib

No dose reductions for trametinib are permitted below 1.5 mg PO daily.

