Hypophysitis	2-4	Toxicity resolves to Grade 0-1. Therapy with pembrolizumab can be continued while endocrine replacement therapy is instituted	Toxicity does not resolve within 12 weeks of last dose or inability to reduce corticosteroid to 10 mg or less of prednisone or equivalent per day within 12 weeks
Hyperthyroidism	3	Toxicity resolves to Grade 0-1	Toxicity does not resolve within 12 weeks of last dose or inability to reduce corticosteroid to 10 mg or less of prednisone or equivalent per day within 12 weeks
	4	Permanently discontinue	Permanently discontinue
Hypothyroidism		Therapy with pembrolizumab can be continued while thyroid replacement therapy is instituted	Therapy with pembrolizumab can be continued while thyroid replacement therapy is instituted
2 ^b T Infusion		Toxicity resolves to Grade 0-1	Permanently discontinue if toxicity develops despite adequate premedication
Reaction	3-4	Permanently discontinue	Permanently discontinue
Pneumonitis	neumonitis 2 Toxicity resolves to Grade 0-1		Toxicity does not resolve within 12 weeks of last dose or inability to reduce corticosteroid to 10 mg or less of prednisone or equivalent per day within 12 weeks
	3-4	Permanently discontinue	Permanently discontinue
Nephritis or inabi		Toxicity does not resolve within 12 weeks of last dose or inability to reduce corticosteroid to 10 mg or less of prednisone or equivalent per day within 12 weeks	
	3-4	Permanently discontinue	Permanently discontinue
All Other Drug- Related Toxicity ^c	3 or Severe	Toxicity resolves to Grade 0-1	Toxicity does not resolve within 12 weeks of last dose or inability to reduce corticosteroid to 10 mg or less of prednisone or equivalent per day within 12 weeks
	4	Permanently discontinue	Permanently discontinue

Note: Permanently discontinue for any severe or Grade 3 drug-related AE that recurs or any life-threatening event.

In case toxicity does not resolve to Grade 0-1 within 12 weeks after last infusion, trial treatment should be discontinued after consultation with the Sponsor Investigator. Subjects who require corticosteroids to manage drug-related adverse events must be at an equivalent dose of ≤10mg per day of prednisone to resume dosing with pembrolizumab. Furthermore, an inability to reduce

^a For patients with liver metastasis who begin treatment with Grade 2 AST or ALT, if AST or ALT increases by greater than or equal to 50% relative to baseline and lasts for at least 1 week then patients should be discontinued.

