b If symptoms resolve within one hour of stopping drug infusion, the infusion may be restarted at 50% of the original infusion rate (e.g., from 100 mL/hr to 50 mL/hr). Otherwise dosing will be held until symptoms resolve and the subject should be premedicated for the next scheduled dose; Refer to Table 3 – Infusion Treatment Guidelines for further management details.

^c Patients with intolerable or persistent Grade 2 drug-related AE may hold study medication at physician discretion. Permanently discontinue study drug for persistent Grade 2 adverse reactions for which treatment with study drug has been held, that do not recover to Grade 0-1 within 12 weeks of the last dose.

the corticosteroid dose for managing a drug-related adverse event to the equivalent of \leq 10 mg prednisone per day within 12 weeks of last pembrolizumab dose should result in permanent discontinuation from pembrolizumab. With investigator and Sponsor Investigator agreement, subjects with a laboratory adverse event still at Grade 2 after 12 weeks may continue treatment in the trial only if asymptomatic and controlled. For information on the management of adverse events, see Section 5.7.2.

In subjects who continue on pembrolizumab having experienced a Grade 3, Grade 4, or persistent (> 4 weeks) Grade 2 drug-related AE, once the subject has recovered from the AE to Grade 0-1, the dosing interval in subsequent cycles may be increased by 1 week (e.g., to every 4 week dosing in subjects who were on an every 3 week schedule). However, in subjects who experience Grade 3 or 4 pneumonitis, or recurrent persistent (>4 weeks) Grade 2 drug - related pneumonitis after rechallenge from a prior episode of persistent (> 4 weeks) Grade 2 drug-related pneumonitis, pembrolizumab must be permanently discontinued.

For subjects who experience a recurrence of the same AE(s) at the same grade or greater with rechallenge of pembrolizumab, a consultation between the Sponsor Investigator and investigator should occur to determine whether the subject should continue in the trial. However, for a subject who experiences a recurrence of the same serious adverse event at the same grade or greater with rechallenge of pembrolizumab, the subject must discontinue pembrolizumab.

Table 6 Dose Modification Guidelines for Trametinib for Drug-Related Adverse Events (Unless Otherwise Specified)

Grade (CTC-AE)*	Dose Modifications
Grade 1 or Grade 2 (Tolerable)	Continue treatment and monitor as clinically indicated.

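### The Table 5 note permanently stops pembrolizumab for recurrent Grade 3 and life-threatening events, but other text in Section 5.2.1.2 allows continuation for non-serious recurrent Grade 3 events and for Grade 4 in two endocrine rows

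*Combined protocol and SAP*

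**What the plan says.** Section 5.2.1.2 opens by making Table 5 binding for withholding pembrolizumab. The note below the table reads "Permanently discontinue for any severe or Grade 3 drug-related AE that recurs or any life-threatening event".

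The paragraphs after the table add three statements:

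- When the same event returns on rechallenge at an equal or higher grade, the instruction is that "a consultation between the Sponsor Investigator and investigator should occur to determine whether the subject should continue in the trial".
- The next sentence, for a serious event: "recurrence of the same serious adverse event at the same grade or greater with rechallenge of pembrolizumab, the subject must discontinue pembrolizumab".
- On dosing interval, a paragraph that begins "In subjects who continue on pembrolizumab having experienced a Grade 3, Grade 4, or persistent (> 4 weeks) Grade 2 drug-related AE". Once such patients have recovered, it permits, but does not require, a one-week longer interval.

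Three rows of Table 5 matter here:

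- Hypophysitis is held at Grades 2-4, with restart on recovery to Grade 0-1. The row adds "Therapy with pembrolizumab can be continued while endocrine replacement therapy is instituted".
- New-onset type 1 diabetes, or Grade 3-4 hyperglycemia with signs of beta-cell failure, is held and then resumed once the patient is stable.
- Hyperthyroidism is held at Grade 3 with restart on recovery, and is a permanent stop at Grade 4.

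Table 20 in Section 7.2.4 describes Grade 4 as having life-threatening consequences. After Table 6, one sentence tells sites to follow Tables 5 and 6 unless later text specifies otherwise.

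**The concern.** The note is absolute, while the rows and paragraphs around it are conditional. An investigator who reads only the note stops pembrolizumab for good. One who reads the row or the paragraph may restart it. The trial registers patients at more than one site, so the same event could be handled in two ways.

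The consequences go beyond the individual patient. Section 5.8 makes unacceptable adverse experiences, as described in Section 5.2.1.2, a reason for mandatory discontinuation from the trial. Table 20 refers approval of certain rechallenges back to the dose modification guidelines, which is the section in conflict. Safety and tolerability are the primary objective (Section 3.1). The RP2D may depend on later-cycle toxicity (end of Section 5.4), and tolerability enters the choice between the two sequences (Section 8.0).

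**Working it through.** No arithmetic applies: the plan states no figure on this point and gives no event rates. The check sets each case under the note and under the other text.

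| Case | Table 5 note | Other text in Section 5.2.1.2 | Result |
|---|---|---|---|
| Non-serious drug-related Grade 3 event recurs at Grade 3 on rechallenge | Permanent stop | Consultation on whether the patient stays in the trial | Conflict |
| Serious Grade 3 event recurs at the same or a higher grade | Permanent stop | Pembrolizumab must stop | Agree |
| Grade 4 hypophysitis | Permanent stop, as life-threatening | Restart on recovery, or continue with hormone replacement | Conflict |
| Grade 4 hyperglycemia with signs of beta-cell failure | Permanent stop, as life-threatening | Resume once stable | Conflict |
| Grade 4 hyperthyroidism | Permanent stop | Permanent stop | Agree |
| Grade 4 drug-related event in general | Permanent stop | Interval paragraph assumes some patients continue | Conflict in wording |

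**Recurrent Grade 3.** Hyperthyroidism gives a clean example. Its row allows restart after Grade 3, so rechallenge can happen. If it recurs at Grade 3 and is not serious, the note stops pembrolizumab and the recurrence paragraph sends the case to consultation. That paragraph has no upper grade limit, so Grade 3 falls inside it. The serious-event sentence that follows is worded as a contrast, which leaves non-serious recurrences on the consultation route.

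**Grade 4.** The link is Table 20, which describes Grade 4 as life-threatening. Neither row separates Grade 4 from the lower grades it lists. The hypothyroidism row shows no readable grade in the text available, so nothing here rests on it.

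**Does any text rank these provisions?** The sentence after Table 6 yields only to what stands below it. The recurrence and interval paragraphs stand above it. It treats Table 5 as a unit, so it cannot rank the note against the table's own rows.

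**Can the rows be read as silent exceptions?** Where an exception to a permanent stop is intended in the AST/ALT/bilirubin row, that row points to a footnote. The hypophysitis and diabetes rows have no such pointer, and the note lists none. Apart from that flagged exception, every other Table 5 row with a readable Grade 4 entry already requires a permanent stop. For Grade 4 within Table 5, the note's life-threatening clause therefore adds something mainly in the rows it contradicts.

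**The case against.** The best case for the plan has four parts.

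1. *The pointer after Table 6 makes Table 5, with its note, prevail over the text above it.* This has some force for recurrence. But the pointer does not say so expressly, and on that reading the consultation paragraph is still contradicted for Grade 3. It does nothing for the note against the rows.
2. *The recurrence paragraph covers all grades and the note is the specific rule for Grade 3. Consultation also concerns staying in the trial, not receiving more pembrolizumab.* The wording does differ, and trametinib can continue after pembrolizumab ends at 24 months. Yet the next sentence singles out serious events for a mandatory pembrolizumab stop, which would be hard to explain if non-serious Grade 3 recurrences already required one.
3. *Life-threatening has a narrower meaning in the seriousness part of Table 20, namely immediate risk of death, so not every Grade 4 event qualifies.* This is arguable and would shrink the Grade 4 conflict. It would not remove it, because the two rows make no such distinction.
4. *Divergence between sites is limited.* Consultation goes to one Sponsor Investigator, rechallenge after certain serious events needs advance approval, and investigators hold protocol meetings. These soften the consequences but do not settle the text.

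Several stronger readings are tempting and not supported:

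- A reader might infer that all endocrine rows conflict with the note. Grade 4 hyperthyroidism agrees with it.
- A reader might infer that any recurrence may continue after consultation. Recurrent serious events must stop under both texts.
- A reader might take recurrent rash as an example. Rash has its own rules in Table 13, below the pointer, so it is not a clean case.
- A reader might extend the diabetes row to all Grade 4 hyperglycemia. The row is limited to cases with signs of beta-cell failure.
- A reader might express one discordant decision as a share of a 12-patient expansion arm. No stated endpoint or decision criterion is a discontinuation rate, so that figure would measure nothing the plan uses.

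**Conclusion.** The contradiction is real but narrow. It covers recurrent non-serious Grade 3 drug-related events, and Grade 4 events in the hypophysitis row and the type 1 diabetes/hyperglycemia row. The interval paragraph's reference to continuing after Grade 4 follows from the same gap. The first part rests on reading the consultation as open to continued pembrolizumab, which the contrast with the serious-event sentence supports. The second rests on the Grade 4 description in Table 20. Its frequency is unknown, because the documents give no rates for these events. Several rows stop pembrolizumab at the first Grade 3 event, so recurrent Grade 3 on rechallenge will arise in only some toxicities. It is more than a clerical matter, because the instruction in doubt is whether a patient may receive the drug again after a severe event. Nothing here says which instruction is clinically right.

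**What to change.** Amend Section 5.2.1.2 so that the Table 5 note, the hypophysitis row, the type 1 diabetes/hyperglycemia row and the recurrence and interval paragraphs agree. Recurrent non-serious Grade 3 events and Grade 4 events in those two rows should each have one instruction. If either row or the consultation route is meant as an exception, name it in the note. Add one sentence stating which text governs if the note, a row and the paragraphs differ. The sponsor and the drug suppliers decide which instruction applies. The change is to the wording of one section and needs no added patients or procedures.

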5.1.2 Subject Inclusion Criteria

In order to be eligible for participation in this trial, the subject must:

- 1. Have histologically or cytologically confirmed non-small cell lung cancer.
- 2. Have stage IV, metastatic or recurrent non-squamous NSCLC with progressive disease after platinum containing chemotherapy (EGFR mutant, ALK, or ROS-1 rearranged NSCLC must have progressed on prior approved TKI's).

- 3. For phase I dose expansion cohorts the patient's tumor must harbor a KRAS mutation detected by a CLIA certified laboratory.
- 4. Be willing and able to provide written informed consent/assent for the trial.
- 5. Be \geq 18 years of age on day of signing informed consent.
- 6. Have measurable disease based on RECIST 1.1.
- 7. Be willing to provide tissue from a newly obtained core or excisional biopsy of a tumor lesion. In the opinion of the investigator, the patient must have tumor accessible by CT or ultrasound guided core biopsy. Subjects for whom newly-obtained samples cannot be provided may submit an archived specimen provided it was obtained after last systemic treatment, within 6 months of signing consent and that tissue is available for either 2 cell blocks or 20 uncut slides (core or excisional biopsy required, fine needle aspirate is not acceptable).
- 8. Have a performance status of 0 or 1 on the ECOG Performance Scale.
- 9. Able to swallow and retain orally administered medication and does not have any clinically significant gastrointestinal abnormalities that may alter absorption such as malabsorption syndrome or major resection of the stomach or bowels.
- 10. Demonstrate adequate organ function as defined in Table 1, all screening labs should be performed within 10 days of treatment initiation.

Table 1. Adequate Organ Function Laboratory Values

System	Laboratory Values
Absolute neutrophil count	$\geq 1.5 \times 10^9 / L$
Hemoglobin	≥9 g/dL
Platelets	≥100 × 10 ⁹ /L
PT/INR and PTT	≤1.5 x ULN
Hepatic	
Albumin	≥2.5 g/dL
Total bilirubin	≤1.5 x ULN
AST and ALT	≤ 2.5× ULN
Renal	
Creatinine or	≤ 1.5 ULN
Calculated creatinine clearance ^a	≥ 50 mL/min
Cardiac	
Left Ventricular Ejection fraction (LVEF)	≥ LLN by ECHO or MUGA ^b

ALT=alanine aminotransferase; AST=aspartate aminotransferase; INR=international normalized ratio;

PT=prothrombin time; PTT=partial thromboplastin time; ULN=upper limit of normal; LLN=lower limit of normal

^a Calculated by the Cockcroft-Gault formula.

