Grade 2 (Intolerable) or Grade 3	Interrupt therapy until toxicity is grade 0-1 and reduce by one dose level when resuming therapy.
Grade 4	Discontinue permanently, or interrupt therapy until Grade 0 to 1 and reduce by one dose level when resuming therapy.

Please follow Table 5 and Table 6 for dose modifications unless specified below.

For Grade \geq 3 drug related adverse events attributed to trametinib both pembrolizumab and trametinib should be simultaneously interrupted with the exceptions shown below.

Except for Grade ≥ 3 lymphopenia

Exceptions where dose modifications are necessary for only trametinib:

- LVEF reduction
- Retinal Vein Occlusion (RVO) and Retinal Pigment Epithelial Detachment (RPED)

Table 7. Trametinib Dose Modification Guidelines and Stopping Criteria for LVEF Decrease

Clinical Evaluation	LVEF-drop (%) or CTCAE grade	Action and Dose Modification
Asymptomatic	Absolute decrease of >10% in LVEF compared to baseline and ejection fraction below the institution's LLN.	 Interrupt trametinib and repeat ECHO/MUGA within 2 weeks.^a If the LVEF recovers within 4 weeks (defined as LVEF ≥LLN and absolute decrease ≤10% compared to baseline): Consult with the Novartis trametinib medical monitor and request approval for restart. Restart treatment with trametinib at reduced dose by one dose level. Repeat ECHO/MUGA 2, 4, 8, and 12 weeks after restart; continue in intervals of 12 weeks thereafter. If LVEF does not recover within 4 weeks: Consult with cardiologist. Permanently discontinue trametinib. Report as SAE Repeat ECHO after 2, 4, 8, 12, and 16 weeks or until resolution.
Symptomatic ^b	 Grade 3: resting LVEF 39-20% or >20% absolute reduction from baseline Grade 4: Resting LVEF ≤20%. 	 Permanently discontinue trametinib. Report as SAE. Consult with cardiologist. Repeat ECHO/MUGA after 2, 4, 8, 12, and 16 weeks or until resolution.

^a If ECHO/MUGA does not show LVEF recovery after 2 weeks, repeat ECHO/MUGA 2 weeks later.

^b Symptoms may include: dyspnea, orthopenea, and other signs and symptoms of pulmonary congestion and edema.

Table 8. Trametinib Withholding and Stopping Criteria for QTc Prolongation

Prolongation*	Action and Dose Modification

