- 12. ECHO/MUGA will be performed every 12-16 weeks unless clinically indicated. The same study should be used for follows that was done for the baseline exam.
- 13. EKG at baseline, C1D1, C2D1, C3D1. Then every 12-16 weeks unless clinically indicated.
- 14. Safety Follow-Up Visit should be conducted approximately 30 days after the last dose of trial treatment or before the initiation of a new anti-cancer treatment, whichever comes first.15. Subjects who discontinue trial treatment for a reason other than disease progression will move into the Follow-Up phase and should be assessed every 9 weeks (63 ±7 days) by radiologic imaging to monitor disease status.
- 16. Once a patient has progression, they will be followed every 12 weeks until death or withdraw from follow-up.

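### Table 7 has no rule for a symptomatic patient with a moderate LVEF fall, and the fallback in Table 6 can be weaker than the rule for the same fall without symptoms

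*Combined protocol and SAP*

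**What the plan says.** Table 7 in Section 5.2.1.2 has two rows.

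- **Asymptomatic.** The trigger is "Absolute decrease of >10% in LVEF compared to baseline and ejection fraction below the" institutional LLN. The first action is "Interrupt trametinib and repeat ECHO/MUGA within 2 weeks". If LVEF recovers within 4 weeks (at or above LLN and no more than 10 points below baseline), restart needs the medical monitor's approval, is one dose level lower, and is followed by ECHO/MUGA at 2, 4, 8 and 12 weeks and then every 12 weeks. If LVEF does not recover within 4 weeks, trametinib stops permanently, with a cardiology consult and an SAE report.
- **Symptomatic.** Two triggers are listed: "Grade 3: resting LVEF 39-20% or >20% absolute reduction from baseline", and Grade 4, which is LVEF of 20% or less. Both lead to permanent discontinuation. The footnote gives dyspnea, orthopnea and signs of pulmonary congestion or edema as examples of symptoms.

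For anything the specific tables do not cover, the instruction is "Please follow Table 5 and Table 6 for dose modifications unless specified below". Table 6 is the trametinib table. For Grade 1 or tolerable Grade 2 it says "Continue treatment and monitor as clinically indicated". For intolerable Grade 2 or Grade 3 it says "Interrupt therapy until toxicity is grade 0-1 and reduce by one dose level when resuming therapy".

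Routine cardiac imaging is set in footnote 12 of the Study Calendar (Section 6.0): "ECHO/MUGA will be performed every 12-16 weeks unless clinically indicated".

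**The concern.** The two rows of Table 7 start at different depths of LVEF loss, and the symptomatic row starts deeper. Between the two thresholds, a patient with symptoms has no row. The stated fallback then makes the outcome depend on one investigator's judgement of grade and tolerability. At the same LVEF, the patient without symptoms has a fixed sequence of interruption, imaging, approval and stopping.

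That reverses the pattern elsewhere in the protocol. In the rest of Table 7, symptoms bring the harsher action. In Table 11, asymptomatic retinal pigment epithelial detachment continues on treatment and symptomatic detachment interrupts.

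The primary objective is safety and tolerability (Section 3.1), and the trial is set up for several sites (Appendix 11.1). A stopping table should give the same answer at each of them. At stake is continued exposure, or a restart without an explicit LVEF criterion, in a patient with cardiac symptoms and a documented LVEF fall.

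**Working it through.** The plan gives no figure to reproduce. The check sets out which LVEF values fall between the rows and compares the required actions.

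**Inputs**

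- Asymptomatic trigger (Table 7): baseline − LVEF > 10, and LVEF < LLN.
- Symptomatic triggers (Table 7): LVEF from 20 to 39, or baseline − LVEF > 20, or LVEF ≤ 20.
- Eligibility (Table 1, and exclusion criterion 21): baseline ≥ LLN.
- LLN: not given. Values of 50%, 53% and 55% are assumed.

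**The uncovered set.** A value that meets the asymptomatic trigger and no symptomatic trigger satisfies

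40 ≤ LVEF < LLN, and 10 < baseline − LVEF ≤ 20.

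In whole percentages, for a given baseline, this runs from max(40, baseline − 20) to min(LLN − 1, baseline − 11).

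**One patient.** Baseline 60%, now 45%, LLN 50%. The fall is 60 − 45 = 15.

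- 15 > 10 and 45 < 50, so the asymptomatic trigger is met.
- 45 is not in 20-39, 15 is not above 20, and 45 is not ≤ 20, so no symptomatic trigger is met.
- Without symptoms, trametinib must be interrupted. With dyspnea or orthopnea, no Table 7 row applies.

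**Uncovered range by baseline**

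| Baseline | LLN 50% | LLN 55% |
|---|---|---|
| 51% | 40% | not eligible |
| 60% | 40-49% | 40-49% |
| 65% | 45-49% | 45-54% |
| 69% | 49% | 49-54% |
| 70% | none | 50-54% |
| 74% | none | 54% |

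At LLN 50% the set is non-empty for baselines 51-69, at LLN 53% for 53-72, and at LLN 55% for 55-74. The widest range at any baseline is 10 whole percentages.

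As a check on the enumeration, count the baseline/LVEF pairs at LLN 50%. Baselines 51 to 60 give 1 + 2 + … + 10 = 55 and baselines 61 to 69 give 9 + 8 + … + 1 = 45, total 100. The same count gives 127 at LLN 53% and 140 at LLN 55%. These are grid cells and say nothing about how often the event occurs.

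**Actions at the same LVEF**

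| | Asymptomatic (Table 7) | Symptomatic, judged Grade 1 or tolerable Grade 2 (Table 6) | Symptomatic, judged intolerable Grade 2 or Grade 3 (Table 6) |
|---|---|---|---|
| Interrupt trametinib | required | not required | required |
| Repeat ECHO/MUGA within 2 weeks | required | not required | not required |
| Condition for restart | LVEF ≥ LLN and ≤ 10 points below baseline, plus medical-monitor approval | does not arise | Grade 0-1 |
| Dose on restart | one level lower | unchanged | one level lower |
| ECHO/MUGA at 2, 4, 8 and 12 weeks after restart | required | does not arise | not required |
| Permanent stop if not recovered at 4 weeks | required | not required | not required |

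No other section supplies the missing row. The separate LVEF bullet in Section 5.2.1.2 says only that LVEF events modify trametinib alone, and the withdrawal criteria in Section 5.8 refer back to Section 5.2.1.2.

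**The case against.** The strongest objection is that continued dosing depends on a grade the documents cannot settle. CTCAE 4.0 is cited but its cardiac criteria are not reproduced. On the general scale in Table 20, Grade 1 means no intervention is indicated, which sits poorly with symptoms of pulmonary congestion, and an event for which hospitalization is indicated would be Grade 3 and force an interruption. Continuation is then plausible mainly for tolerable Grade 2. If the event is graded on LVEF, recovery to Grade 0-1 may itself require some LVEF recovery.

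This narrows the consequence. It does not close the gap: tolerable Grade 2 remains, and the interruption route still lacks timed imaging, medical-monitor approval and the 4-week stop. Table 6 states no LVEF criterion for restart, and whether Grade 0-1 would match Table 7's recovery definition cannot be determined from the documents.

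A second objection is that general safeguards exist. The investigator may withdraw a subject for any untoward effect (Section 5.8). Grade 2 or greater non-hematological toxicity can be judged dose limiting (Section 5.4). Visits are weekly in the first trametinib cycle and the first combination cycle, adverse events are discussed at least monthly (Section 10.5), and ECHO/MUGA can be done when clinically indicated. These make unmanaged symptoms less likely, but they are discretionary or general, and none fixes an action or imaging date for this patient.

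Third, the affected group is narrow. In lung cancer, dyspnea attributed to the tumour might leave a patient in the asymptomatic row. That is a fair limit on size. A sensible clinician might also treat the asymptomatic row as a minimum, but the row's label does not say so.

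**Conclusion.** The concern holds. Table 7 omits symptomatic patients with a fall of more than 10 and up to 20 points and LVEF from 40% to below LLN, and the written fallback can give them a weaker mandatory action than an asymptomatic patient with the same LVEF. Confidence in the gap is high: it follows from the text for any LLN above 40%. Its exact width rests on the assumed LLN of 50-55%. Continued dosing is conditional on the event being judged Grade 1 or tolerable Grade 2. The loss of Table 7's timed follow-up applies on either Table 6 route.

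The number of patients affected cannot be estimated and may be small. The point concerns patient safety and leaves the sample size, dose-escalation rule and efficacy analyses unchanged. It should be corrected because the correction is cheap.

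**What to change.** Add one row to Table 7. A symptomatic patient who meets the asymptomatic threshold (a fall of more than 10 points and LVEF below LLN) but not Grade 3 or 4 receives at least the asymptomatic row's actions: interrupt trametinib, repeat ECHO/MUGA within 2 weeks, and follow the same restart conditions and 4-week discontinuation rule. The sponsor may choose something stricter, such as an immediate cardiology consult. Table 6 stays as the default for LVEF patterns that Table 7 still does not list.

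The cost is one table row in a protocol amendment. For an affected patient it means an interruption, repeat imaging, medical-monitor approval and a one-level reduction on restart. Under Table 4 that reduction means discontinuation for a patient already at 1.5 mg on Days 1-7. The protocol already imposes the same burden on patients without symptoms.
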